11.7.2 Secondary Endpoints

11.7.2.1 SRI(4) Response at Week 48

SRI(4) response at week 48 is defined in an analogous way as SRI(4) response at week 32 (see details in 12.7.1).

Similar analyses will be conducted as for the primary endpoint, including the primary analysis and sensitivity analysis.

Sponsor: Bristol-Myers Squibb
Protocol no: IM011021

11.7.2.2 BICLA Response at Week 48

All subjects in the randomized population will be categorized as a responder or non-responder. A subject will be considered a BICLA Week 48 responder if all of the following criteria are met. If one criterion is not met, the subject will be considered a BICLA Week 48 non-responder.

- Improvement in all organ systems with activity graded as BILAG-2004 A or B at baseline
 - This criterion is met if both of the following conditions are met: All organ domains with an A grade at baseline are graded B, C, D, or E at Week 48
 - All organ domains with an B grade at baseline are graded C, D, or E at Week 48
- No new organ system with activity graded as BILAG A and no more than 1 new organ system with activity graded as BILAG B
An A grade is new if the baseline grade for the same organ system was B, C, D or E. A B grade is new if the baseline grade for the same organ system was C, D, or E.

This criterion is met if both of the following conditions are met:

- There are no organ domains with an A grade at Week 48
 - The number of organ domains with a B grade at Week 48 that were graded C, D, or E at baseline is ≤ 1
- No increase from baseline in SLEDAI-2K (≤ 0 points for change from baseline score)
SLEDAI-2K score at Week 48 - SLEDAI-2K score at baseline ≤ 0
 - No increase $\geq 10\%$ (or ≥ 0.3 points) in the Physician's Global Assessment of Disease Activity on a 3-point VAS:
Physician's Global Assessment of Disease Activity at Week 48 – Baseline Physician's Global Assessment of Disease Activity < 0.3
 - No discontinuation of IP or use of prohibited/restricted medications beyond the protocol allowed threshold before assessment.

- No discontinuation of IP is defined as remaining on IP within 14 (≤ 14) days prior to the Week 48 visit. Treatment discontinuation date is captured in the eCRF.
- Restricted/prohibited medications are defined as in [section 11.7.1](#) and are:
 - Corticosteroid dosages above 7.5mg/day prednisone or equivalent after week 20 (Week 20+1 day)
 - Use of IM or IV CS within 8 weeks before the W32 and W48 assessment timepoints
 - Use of IA or intrabursal CS within 8 weeks before the W32 and W48 assessment timepoints
 - Use of modified-release oral CS formulations within 8 weeks before the W32 and W48 assessment timepoint
 - Addition of topical CS within 2 weeks before the W32 and W48 assessment timepoint
 - Ocular CS are allowed for non-SLE indications
 - Inhaled CS are allowed

- More than 1 CS burst or any CS burst for treatment of SLE after week 8

Sponsor: Bristol-Myers Squibb
Protocol no: IM011021

- Oral steroid burst for non-SLE indication is permitted up to week 24 or between week 32 and week 40
- Initiation of or increases in oral NSAIDs occurring within the 7 days before the W32 and W48 assessment timepoints
- Initiation of or increase in immunosuppressant regimen and/or antimalarial dosage/regimen
 - Dose decrease or discontinuation is permitted
 - Discontinuation with restart at the same or lower dose is permitted
 - Immunosuppressants are defined as (combinations of these are not permitted): Azathioprine, 6-MP, methotrexate, leflunomide, MMF
 - Antimalarials are defined as: chloroquine, hydroxychloroquine, or quinacrine
- Any medications included in protocol Appendix 7 between first dose date and efficacy assessment visit

Similar analyses will be conducted as for the primary endpoint, including the primary analysis and sensitivity analysis.

11.7.2.3 CLASI-A Response (CLASI-50) at Week 48

Subjects who have a baseline CLASI activity score ≥ 10 will be included in this analysis. Subjects meeting this criterion will be categorized as CLASI-A responders or non-responders. Responders are defined as subjects who have at least a 50% decrease in their CLASI activity score at Week 48.

$$\frac{\text{CLASI activity score at Week 48} - \text{CLASI activity score at baseline}}{\text{CLASI activity score at baseline}} \times 100 \leq -50$$

Subjects not meeting this criterion will be considered non-responders.

Similar analyses will be conducted as for the primary endpoint, including the primary analysis and sensitivity analysis.

11.7.2.4 LLDAS Response at Week 48

A subject is considered an LLDAS responder at Week 48 if all of the following criteria are met:

- SLEDAI-2K ≤ 4 , with no activity in major organ systems (renal, central nervous system, cardiopulmonary, vasculitis, fever) and no hemolytic anemia or gastrointestinal activity (measured as maintaining a D or E score in the BILAG gastrointestinal body system)

This definition will be implemented as follows:

- SLEDAI-2K ≤ 4
 - The following items on the SLEDAI-2K are scored as 'no': seizure, psychosis, organic brain syndrome, visual disturbance, cranial nerve disorder, lupus headache, CVA (cerebrovascular accident), vasculitis, urinary casts, hematuria, proteinuria, pyuria, pleurisy, pericarditis, and fever
 - No hemolytic anemia on BILAG (item 96 on BILAG)
 - All BILAG gastrointestinal items scored as 0 (all items under gastrointestinal organ system graded D or E)
- No new lupus disease activity compared with the previous assessment measured as no new or worsening individual BILAG parameter

This definition will be implemented as follows:

- None of the 97 BILAG items are scored 4 (=worse) or 5 (=new)
- None of the 97 BILAG items are newly marked abnormal SLE related

Sponsor: Bristol-Myers Squibb
Protocol no: IM011021

If an item is rated Abnormal SLE Related at a visit then it must have been rated Abnormal SLE related at the previous visit.

- Physician's Global Assessment of Disease Activity ≤ 1
- Prednisone or equivalent dose ≤ 7.5 mg/day
- Well tolerated standard maintenance doses of immunosuppressive drugs and approved biologic agents

Similar analyses will be conducted as for the primary endpoint, including the primary analysis and sensitivity analysis.

11.7.2.5 Tender and Swollen Joint Count at Week 48

The change from baseline in counts for tender, swollen, and tender + swollen (active) joints will be calculated on all subjects in the randomized population.

- Tender 40-joint count at Week 48 – tender 40-joint count at baseline
- Swollen 40-joint count at Week 48 – swollen 40-joint count at baseline
- Tender + swollen (active) 40-joint count at Week 48 - tender + swollen 40-joint count at baseline

[figure not shown]
Analyses of each of these three endpoints will be conducted using a mixed model repeated measures (MMRM) model. For analysis visits where the NRI-imputation criteria are met (see [section 11.7.1](#)), no imputation is applied but the observed values are set missing. The MMRM model will include the fixed categorical effects of treatment group, analysis visit (Week 24, 32 and 48), treatment-by-analysis visit interaction, randomization stratum defined in [section 6.5](#) and the continuous fixed covariate of baseline endpoint. An unstructured covariance matrix will be used to model the correlation of the repeated measures within each subject. The parameter estimations will be based on the assumption of data being missing at random (MAR) and using the method of restricted maximum likelihood (REML). The denominator degrees of freedom will be calculated using the Kenward-Rogers method. Adjusted mean changes (LSMEANS) with corresponding SE and 95% CI per treatment arm will be reported. The difference in adjusted means (LSMEANS) between BMS-986165 and placebo at the predefined time point, and corresponding 95% CI and p-value based on this longitudinal repeated measures model will be provided. In case of non-convergence of the preferred longitudinal model, memory space issues, or other computational issues the following covariance structures will be used in order of preference (decreasing number of parameters to be estimated): heterogeneous toeplitz, heterogeneous compound symmetry, and compound symmetry.

A longitudinal plot of mean change from baseline in tender joint count, swollen joint count, and tender +swollen joint count with standard errors by treatment group will be provided.

[figure not shown]
A sensitivity analysis will be conducted similar to the primary endpoint (treatment policy strategy).

Sponsor: Bristol-Myers Squibb

Protocol no: IM011021

[figure not shown]
Sponsor: Bristol-Myers Squibb
Protocol no: IM011021

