9.3.1 Efficacy Analysis

9.3.1.1 Endpoints

Primary Efficacy Endpoint

[figure not shown]
The primary efficacy endpoint is:

- Proportion of subjects who meet SRI(4) response at Week 32 (SRI response is defined in [Section 8.1](#))

Secondary Efficacy Endpoints

Secondary efficacy endpoints are as follows:

- Proportion of subjects who meet SRI(4) response at Week 48
- Proportion of subjects who achieve BICLA response at Week 48, where BICLA response is defined as follows:
 - Improvement in all organ systems with activity graded as BILAG-2004 A or B at baseline
 - No new organ system with activity graded as BILAG A; no more than 1 new organ system with activity graded as BILAG B
 - No increase from baseline in SLEDAI-2K (≤ 0 points for change from baseline score)
 - No increase $\geq 10\%$ in the Physician's Global Assessment of Disease Activity on a 3-point VAS
 - No discontinuation of IP or use of restricted medications beyond the protocol allowed threshold before assessment
- Proportion of subjects who achieve LLDAS at Week 48
- Proportion of subjects with a CLASI activity score ≥ 10 at baseline who achieve a CLASI response, defined as a decrease of $\geq 50\%$ from baseline CLASI activity score at Week 48
- Change from baseline in the 40-joint count for tender, swollen, and tender + swollen joints at Week 48

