The number and percentage of subjects achieving NRI-imputed SRI(4) response at Week 32 and those who do not will be reported by treatment group with the estimated response rate and asymptotic 95% confidence intervals (CIs). Differences in response rates between each active treatment group and placebo with corresponding 2-sided 95% CIs based on the continuity-corrected Newcombe method will also be provided.

Tipping Point Analysis

Tipping point analysis will further be used to assess the robustness of the primary study results. Different number of events between treatment groups will be assessed until the study conclusion is

Sponsor: Bristol-Myers Squibb
Protocol no: IM011021

changed. Each imputed value is initially imputed as a responder. The imputed values in the placebo group will remain as responders while the BMS-986165 imputed values are replaced as a non-responders one at a time, therefore changing the number of events between groups. Once all imputed values in the BMS-986165 group have been replaced with non-responders values, the data will reset to where the BMS-986165 group imputed values are all responders and one by one the imputed values in the placebo group are replaced with a non-responder until all placebo are non-responders and all BMS-986165 are responders. Furthermore, every pair of imputations between the placebo and BMS-986165 groups will be assessed similarly, creating a matrix of possible patterns.

At each iteration, the statistical analysis is assessed, and the direction of the analysis is recorded. A graph will be provided to identify at what point to which the difference in events cause a direction shift in study results. The tipping point analyses will be based on a two-sample chi-square test approach rather than a stratified CMH test approach for simplicity of the analysis.

Sensitivity analysis #1 (Treatment Policy Strategy)

The primary analysis for the primary endpoint will be repeated using a treatment policy estimand approach (Intention-To-Treat (ITT) principle). For this approach, subjects will only be imputed as non-responders if there is a missing value for the endpoint at the considered timepoint.

Sensitivity analysis #2

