The primary analysis for the primary endpoint will be repeated, however the NRI imputation method will be modified. The prohibition medications restriction for the NRI imputation method will not apply. That is, subjects who take any of the prohibited medications listed above will not be imputed as non-responders. Subjects will continue to be imputed as non-responders if any of the following apply:

- Permanent treatment discontinuation of IP before the considered time point
- Missing value for the endpoint at the considered time point
- Subjects who are lost to follow-up or discontinue the study early are considered non-responders for all time points at and after loss to follow up or study discontinuation

Supportive Analysis #1 – Assessment of Covid-19 related impact

For this supportive analysis, the primary analysis for the primary endpoint will be repeated, but observations that were missed due to the impact of COVID-19 will be imputed with the last value observed before the visit that was missed due to COVID-19 restrictions.

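### For Week 48 BICLA, sensitivity analyses #1 and #2 do not relax the prohibited-medication rule, because that rule is also a criterion of the endpoint itself

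*SAP*

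**What the plan says.** Protocol 9.3.1.1, SAP 6.2 and SAP 11.7.2.2 all define BICLA response by five criteria. The first four are clinical: BILAG improvement, limits on new BILAG A and B grades, SLEDAI-2K, and the physician's global assessment. The fifth is not clinical. The protocol words it as "No discontinuation of IP or use of restricted medications beyond the protocol allowed threshold before assessment", and SAP 11.7.2.2 as "No discontinuation of IP or use of prohibited/restricted medications beyond the protocol allowed threshold before assessment". All five are required: "If one criterion is not met, the subject will be considered a BICLA Week 48 non-responder".

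SAP 11.7.2.2 then spells out criterion 5. On study drug (IP): "No discontinuation of IP is defined as remaining on IP within 14 (≤ 14) days prior to the Week 48 visit". On medication, it points back to the list in SAP 11.7.1, which is the non-responder imputation (NRI) list for SRI(4), and itemises it.

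The section closes with "Similar analyses will be conducted as for the primary endpoint, including the primary analysis and sensitivity analysis". The two sensitivity analyses are described in SAP 11.7.1:

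- **#1, treatment policy:** "For this approach, subjects will only be imputed as non-responders if there is a missing value for the endpoint at the considered timepoint".
- **#2, medication rule dropped:** "subjects who take any of the prohibited medications listed above will not be imputed as non-responders". Permanent IP discontinuation, study withdrawal or loss to follow-up, and a missing value remain non-response.

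SAP 7.2 adds a rule for all endpoints: only efficacy data taken no later than the last dose are assigned to an analysis visit.

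**The concern.** For SRI(4), a prohibited medication affects the result only through NRI. Once that rule is relaxed, the observed response counts. For BICLA the same event acts twice, through NRI and through criterion 5. The sensitivity analyses switch off the first route and leave the second in place.

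Week 48 BICLA is in the multiplicity-controlled set (SAP 5.4.1), and the treatment-policy analysis was added deliberately (SAP 5.4.2). If the BICLA tables agree, they can be taken to show that the result does not depend on how rescue and other prohibited medication is handled. The analyses could hardly have shown anything else.

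The subjects concerned should exist in the data. Protocol 6.4 keeps subjects on assigned treatment through flares and failed tapers. Protocol 6.7.3 keeps those who miss the Week 20 steroid target on treatment but counts them as non-responders.

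**Working it through.** The plan states no figure on this point, so the check is one of logic. Take a subject who meets BICLA criteria 1 to 4 at Week 48. Cross IP status with a listed medication event, and classify the subject (1 = responder, 0 = non-responder) under these rules:

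- **Endpoint as written:** 0 if a listed medication was taken or IP was stopped more than 14 days before the visit; otherwise 1 if the value is observed.
- **Main analysis:** 0 if the value is missing, IP was permanently stopped or a listed medication was taken; otherwise the endpoint value.
- **#1:** 0 only if the value is missing; otherwise the endpoint value.
- **#2:** 0 if the value is missing or IP was permanently stopped; otherwise the endpoint value.

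For subjects who stopped IP, the Week 48 assessment is taken to fall after the last dose. The SAP 7.2 cut then makes it missing. Each cell shows main / #1 / #2.

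| Case | SAP as written, cut applied | SAP as written, cut lifted |
|---|---|---|
| On IP, no listed medication | 1 / 1 / 1 | 1 / 1 / 1 |
| On IP, listed medication | 0 / 0 / 0 | 0 / 0 / 0 |
| Stop within 14 days, no medication | 0 / 0 / 0 | 0 / 1 / 0 |
| Stop within 14 days, medication | 0 / 0 / 0 | 0 / 0 / 0 |
| Stop more than 14 days before, no medication | 0 / 0 / 0 | 0 / 0 / 0 |
| Stop more than 14 days before, medication | 0 / 0 / 0 | 0 / 0 / 0 |

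**Medication events.** The second row is the finding. SRI(4) has no medication criterion, so the same subject, if a clinical SRI(4) responder, is 0 / 1 / 1. The failure on medication is specific to BICLA.

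**IP discontinuation.** #2 gives 0 by design for both endpoints. In #1, the last-dose cut makes the later value missing, and missing is non-response. This holds for SRI(4) as well.

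**Removing criterion 5 from the sensitivity analyses.**

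- With the cut kept, only the second row changes, to 0 / 1 / 1.
- With the cut also lifted for #1, every row with an IP stop becomes 0 / 1 / 0.

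**Two edges.**

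- *14-day tolerance.* The Week 48 window is Days 324 to 351, with target Day 337. A subject assessed on Day 328 with last dose on Day 330 keeps the value and meets criterion 5. If the NRI time point means the target day, the main analysis gives 0 and #1 can give 1.
- *Burst above 40 mg/day.* This item is in the 11.7.1 list but not visible in the printed BICLA list. The cross-reference probably covers it, and the gap may be removed text. If it is truly absent, a single such burst that no other item catches (for example one up to Week 8) is a medication event on which #1 and #2 could differ from the main analysis.

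**Size.** Only subjects who meet criteria 1 to 4 and have such an event can move. With about 90 per arm and an assumed share s, the number is 90 × s:

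- s = 5%: 90 × 0.05 = 4.5
- s = 10%: 90 × 0.10 = 9
- s = 20%: 90 × 0.20 = 18

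**The case against.** Criterion 5 comes from the protocol, so BICLA is a composite by intent, and criteria 1 to 4 alone are a different endpoint. That stands for the main analysis, which should not change. It does not rescue a sensitivity analysis whose stated purpose is to set these events aside.

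The carry-over wording is loose. Because the BICLA list is tied to 11.7.1, a programmer could carry the waiver in #2 into criterion 5. That is a possible reading, but the SAP does not state it: #2 speaks of who is imputed, and criterion 5 makes a subject a non-responder by definition. Following the text gives an uninformative table, and departing from it is an unspecified choice.

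Three stronger readings are tempting, and the documents do not support them.

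- **That the BICLA sensitivity analyses can never differ from the main one on IP discontinuation, and that this is a BICLA defect.** #2 retains that rule on purpose, the 14-day tolerance leaves a narrow exception in #1, and the last-dose cut applies to every endpoint.
- **That #1 is a clean treatment-policy analysis for SRI(4).** It works there for medication events, but not for IP stops followed by later assessments.
- **That everyone with an event would be reclassified.** An assumed event rate of 20 to 30% would be 18 to 27 of 90 per arm, but this includes subjects who fail criteria 1 to 4 anyway and IP stops that #2 is meant to keep as failures. Criterion 5 also does not catch every event: steroid injections count only within 8 weeks of the assessment, added topical steroids within 2 weeks, oral NSAID changes within 7 days, and some bursts are permitted.

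**Conclusion.** The point holds for medication events. Read as written, a subject with a listed medication event is a BICLA non-responder in all three analyses. #2 therefore essentially reproduces the main analysis, and #1 is not treatment-policy for medication. The possible exception is the burst item above 40 mg/day.

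For IP discontinuation the claim is narrower. #2 behaves as designed. #1 is blocked twice: by criterion 5, apart from stops within 14 days of the visit, and by the SAP 7.2 last-dose cut, which limits SRI(4) in the same way.

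The logic needs no event rate. The size does, and the documents give none: about 4.5 to 18 of 90 per arm if 5 to 20% of subjects (assumed) meet criteria 1 to 4 and have such an event. For #2 only those with a medication event count. This should be corrected. The main BICLA result is not affected.

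**What to change.** Keep the main BICLA definition and add to SAP 11.7.2.2:

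- **For #2,** the medication part of criterion 5 does not apply. IP discontinuation, study withdrawal and missing data remain non-response.
- **For #1,** BICLA is derived from criteria 1 to 4 only, and only missing Week 48 data count as non-response. Week 48 assessments collected after the last dose are used, as a stated exception to the SAP 7.2 cut. Without that exception the change restores medication events only.

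The cost is SAP wording, one derived variable and the windowing exception for #1. No protocol change is needed. If the sponsor prefers not to do this, the SAP should say that #1 and #2 are not informative for BICLA on these events.

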11.7.1 Primary Endpoint

The primary efficacy endpoint is the proportion of subjects who have a SRI(4) response at Week 32 as per non-responder imputation. All subjects in the randomized population will be categorized as a responder or non-responder.

Definition of Endpoint

A responder is defined as meeting all of the following criteria. If one criterion is not met, the subject will be considered a non-responder.

- Reduction from baseline of ≥ 4 points in the SLEDAI-2K

The total SLEDAI-2K score is the sum of the scores for all items. The total score will be taken from the eCRF. A reduction in at least 4 points is achieved if SLEDAI-2K at Week 32 – SLEDAI-2K at baseline ≤ -4 .

- No new BILAG A (severe disease activity) and not more than 1 new BILAG B (moderate disease activity) organ domain grade

An A grade is new if the baseline grade for the same organ system was B, C, D or E. A B grade is new if the baseline grade for the same organ system was C, D, or E.

This criterion is met if both of the following conditions are met:

- All organ domains with an A grade at Week 32 were graded A at baseline
- The number of organ domains with a B grade at Week 32 that were graded C, D, or E at baseline is ≤ 1

- No worsening from baseline in the Physician's Global Assessment of Disease Activity scale by at least 0.3 points
 - Physician's Global Assessment of Disease Activity at Week 32 – Baseline Physician's Global Assessment of Disease Activity < 0.3

Non-Responder Imputation (NRI) Method

Subjects will be considered non-responders at a given time point per imputation (i.e. regardless of observed SRI-response as defined above) if any of the following apply:

- Subject takes any of the following prohibited medications:
 - Corticosteroid dosages above 7.5mg/day prednisone or equivalent after week 20 (Week 20+1 day)
 - Use of IM or IV CS within 8 weeks before the W32 assessment timepoint
 - Use of IA or intrabursal CS within 8 weeks before the W32 assessment timepoint

Sponsor: Bristol-Myers Squibb
Protocol no: IM011021

- Use of modified-release oral CS formulations within 8 weeks before the W32 assessment timepoint
- Addition (compared to baseline) of topical CS within 2 weeks before the W32 assessment timepoint
 - Ocular CS are allowed for non-SLE indications
 - Inhaled CS are allowed
- CS bursts/rescue above the protocol-defined maximum dosage (40 mg/day prednisone equivalent)
- More than 1 CS burst or any CS burst for treatment of SLE after week 8

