 - Oral steroid burst for non-SLE indication is permitted up to week 24 or between week 32 and week 40
- Initiation of or increases in oral NSAIDs (compared to baseline) occurring within the 7 days before the W32 assessment timepoint
- Initiation of or increase in immunosuppressant dosage/regimen and/or antimalarial dosage/regimen (compared to baseline)
 - Dose decrease or discontinuation is permitted
 - Discontinuation with subsequent restart at the same or lower dose is permitted
 - Immunosuppressants are defined as (combinations of these are not permitted): Azathioprine, 6-MP, methotrexate, leflunomide, MMF
 - Antimalarials are defined as: chloroquine, hydroxychloroquine, or quinacrine
- Subjects takes any medications included in protocol Appendix 7 between first dose date and efficacy assessment visit
- Permanent treatment discontinuation of IP before the considered time point
- Missing value for the endpoint at the considered time point
- Subjects who are lost to follow-up or discontinue the study early are considered non-responders for all time points at and after loss to follow up or study discontinuation

Primary Analysis

The primary analysis will be conducted on the randomized population.

The analysis of NRI-imputed SRI(4) response at Week 32 will be conducted using logistic regression modeling, with treatment group (four levels) and redefined stratification factor (see [section 6.5](#), thirteen levels) as fixed factors. The odds ratios of response will be estimated and tested between the BMS-986165 treatment groups and the placebo group [REDACTED]. In case the logistic regression model fit is not stable the region stratification factor may be removed from the model (resulting in 5 stratification factors: non-Japan subjects with baseline CS dose ≥ 10 mg/day and SLEDAI-2K score ≥ 10 , non-Japan subjects with baseline CS dose < 10 mg/day and SLEDAI-2K score ≥ 10 , non-Japan subjects with CS dose ≥ 10 mg/day and SLEDAI-2K score < 10 , non-Japan subjects with CS dose < 10 mg/day and SLEDAI-2K score < 10 and Japan subjects). Estimated odds ratios of response with corresponding 2-sided 95% confidence interval (CI) and p-value will be reported.

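### Timed medication look-backs in SAP 11.7.1 name only Week 32, so the joint-count model, taken literally, screens Week 48 on Week 32 exposure; other Week 48 anchors are ambiguous or unwritten

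*SAP*

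**What the plan says.** The non-responder rule in SAP 11.7.1 is framed generally: "Subjects will be considered non-responders at a given time point per imputation". Its timed items are not general:

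- "Use of IM or IV CS within 8 weeks before the W32 assessment timepoint"
- intra-articular and intrabursal injections, on the same terms
- modified-release oral corticosteroids (CS), with the same 8 weeks before Week 32
- "Addition (compared to baseline) of topical CS within 2 weeks before the W32 assessment timepoint"
- for NSAIDs, "Initiation of or increases in oral NSAIDs (compared to baseline) occurring within the 7 days before the W32 assessment timepoint"

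Other items in the list either have no look-back or refer to whichever visit is being considered.

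The Week 48 endpoints connect to this list in different ways:

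- **Joint counts (11.7.2.5).** The repeated-measures model covers Weeks 24, 32 and 48. At any visit where the 11.7.1 criteria are met, "no imputation is applied but the observed values are set missing".
- **BICLA (11.7.2.2).** The restricted medications are said to be those of 11.7.1, but they are written out again with two anchors, for example "Initiation of or increases in oral NSAIDs occurring within the 7 days before the W32 and W48 assessment timepoints". The steroid windows are paired in the same way.
- **SRI(4) (11.7.2.1).** Week 48 is defined by analogy with Week 32, citing a section 12.7.1 that the SAP does not contain.
- **CLASI-50 and LLDAS (11.7.2.3, 11.7.2.4).** The only link is "Similar analyses will be conducted as for the primary endpoint, including the primary analysis and sensitivity analysis".

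SAP 5.4.1 records that non-responder imputation is meant for the primary and secondary endpoints at both Week 32 and Week 48, and that the Week 48 endpoints are in the multiplicity-controlled hierarchy. Protocol 9.3.1.2 counts prohibited medication as non-response with no look-back window.

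**The concern.** A look-back of 7 days, 2 weeks or 8 weeks serves to flag an assessment that may reflect a recently taken drug and not the study treatment. It does that only if it ends at the assessment being analysed. A window that ends at Week 32 says nothing about drug use just before Week 48.

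The same list uses generic timing for other items, so a programmer has some reason to take the named week literally. For the joint counts, that decides which observed values enter a model for a multiplicity-controlled endpoint, and NSAIDs and injected steroids bear directly on those counts. Across the Week 48 endpoints, one subject with one drug record could be handled under different rules, depending on which subsection the programmer follows.

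**Working it through.** No figure in the plan depends on this point, so there is none to reproduce. The check sets the windows out in study days and follows each link.

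**Inputs.** Scheduled days: Week 24 = Day 169 (protocol Table 2), Week 32 = Day 225 and Week 48 = Day 337 (protocol Table 3). Window lengths: 56, 14 and 7 days (SAP 11.7.1). Analysis visit ranges: Week 32 = Days 212 to 239, Week 48 = Days 324 to 351 (SAP 7.2).

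**Step 1: the windows.** Window start = visit day minus length; gap = start of the Week 48 window minus 225.

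| Item | Length (days) | Ending at Week 32 | Ending at Week 48 | Gap (days) |
|---|---|---|---|---|
| Injected and modified-release CS | 56 | 169–225 | 281–337 | 281 − 225 = 56 |
| Added topical CS | 14 | 211–225 | 323–337 | 323 − 225 = 98 |
| Oral NSAID start or increase | 7 | 218–225 | 330–337 | 330 − 225 = 105 |

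No pair overlaps. With the latest Week 32 day and the earliest Week 48 day allowed by SAP 7.2, the longest windows are still apart: (324 − 56) − 239 = 29 days. The choice of anchor therefore changes which exposures are flagged.

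**Step 2: joint counts, read literally.** An NSAID started on Day 332, 5 days before Week 48, is outside Days 218–225, so the Week 48 count stays in the model. An NSAID started on Day 220 is inside Days 218–225, so the criterion is met and the Week 48 count is removed, although the start was 337 − 220 = 117 days earlier. At Week 24 (Day 169) all three Week 32 windows fall on or after the visit, so none works as a look-back.

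**Step 3: BICLA.** The paired wording can mean that either window counts, that both must be met, or that each window belongs to its own visit. The first and third readings cover the Week 48 period; the first also adds Days 169–225, 211–225 and 218–225. Only the second would miss a subject exposed just before Week 48 alone.

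**Step 4: SRI(4), CLASI-50, LLDAS.** The general lead-in in 11.7.1, the analogy for SRI(4) and the statement in SAP 5.4.1 all point to a Week 48 anchor. None of the three subsections writes one.

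**Step 5: illustration of size for BICLA.** Assumptions, not from the documents: 45 of 90 subjects in an arm would otherwise respond, the exposure probability q is the same in each window, and the windows are independent. Subjects turned into non-responders:

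- Week 48 only: 45q
- either window: 45[1 − (1 − q)²]
- both windows: 45q²

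At q = 5% these are 2.25, 4.39 and 0.11. Moving from Week 48 only to either window lowers the arm's rate by:

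- q = 2%: (1.78 − 0.90)/90 = 1.0 points
- q = 5%: (4.39 − 2.25)/90 = 2.4 points
- q = 10%: (8.55 − 4.50)/90 = 4.5 points

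**The case against.** A reader might infer that Week 48 classification as a whole uses the wrong treatment period. The documents do not support that. The BICLA text names Week 48. For SRI(4), and by extension CLASI-50 and LLDAS, the surrounding wording favours re-anchoring; to import the list through a general reference to similar analyses and yet freeze its anchor at Week 32 would be a strained reading.

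A reader might also infer that Week 48 outcomes have no protection from concomitant drugs. That is too strong. The rules on CS above 7.5 mg/day after Week 20, CS bursts, immunosuppressant or antimalarial increases, protocol Appendix 7 drugs and permanent discontinuation are not tied to Week 32. LLDAS has its own CS criterion. Protocol 6.7.1 restricts most of these exposures, although a conduct rule does not classify a subject.

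Nor is it shown to be an error that BICLA fails at Week 48 for use before Week 32. Protocol 9.3.1.2 has no window, so counting earlier use does not contradict it.

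The planned sensitivity analyses help as well: one imputes only missing values, another drops the medication rules, and the joint counts get a treatment-policy analysis. They show whether medication handling drives a result, but they do not define the main analysis. Week 24 is a visit in the model, not a secondary endpoint, so that part is minor.

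What the objection does not remove is the joint-count model. It points straight to a list with an explicit Week 32 anchor, with no analogy wording in between.

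**Conclusion.** The point holds, with different force by endpoint:

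- **Joint counts.** As written, Week 48 values are screened on Week 32-window exposure and not on Week 48-window exposure, and Week 24 has no usable look-back. This is a stated anchor that does not fit the visit, not merely missing detail.
- **BICLA.** The right period is covered. The fault is an extra or ambiguous Week 32 window in a list said to match 11.7.1.
- **SRI(4), CLASI-50, LLDAS.** The Week 48 anchor is implied but unwritten.

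Only the timed items are affected. The documents give neither exposure rates nor a count of affected subjects, so the effect on results cannot be sized. The 1.0 to 4.5 points for BICLA rest on the assumptions in the working and describe one arm's response rate. The treatment difference is biased only if exposure, or response among the exposed, differs by arm. Because these endpoints are in the multiplicity-controlled hierarchy, the rule should be unambiguous before unblinding.

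**What to change.** 1. In SAP 11.7.1 and 11.7.2.2, define each timed look-back relative to the assessment timepoint being analysed.
2. State that this one list applies to SRI(4), BICLA, CLASI-50, LLDAS and each visit in the joint-count model.
3. State whether exposure in a Week 32 window carries forward to Week 48 classification.
4. Reconcile the result with protocol 9.3.1.2, which has no window.
5. Correct the cross-reference to section 12.7.1.

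The cost is SAP wording and one programming parameter. No new data are needed.
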